#### Study Schedule:

Events	Screening Baseline	2-weeks*	6-weeks	3-months	18-weeks**	6-Months
Informed Consent,						
Demographics,	X					
Inclusion/Exclusion Criteria, Medical History, Conmeds						
Demographics/Product Use						
Questionnaire	X					
Dentifrice Distribution	X		X	X	X	
Diary Disbursement/Review	X		X	X	X	X
Update of Inclusion/Exclusion						
Criteria, Medical History and			X	X	X	X
Conmeds						
Oral Soft/Hard Tissue Exam	X		X	X		X
Gingival Exam (MGI)	X		X	X		X
Bleeding Exam (GBI)	X		X	X		X
Plaque Exam (PI)	X		X	X		X
Subjective Sensory Evaluation	X		X	X	X	X
Supervised Brushing	X					
Compliance Check		X	X	X	X	X
Product assessment						X
Questionnaire						Λ
Adverse Events			X	X	X	X
Product Weights	X		X	X	X	X

At 2-weeks, subjects will receive a post-baseline compliance call to reinforce product use instructions and study instructions.

#### VII. SUBJECT ASSIGNMENT TO TREATMENT GROUPS

At the baseline visit, following the clinical assessments, the study population will be evenly distributed into three treatment groups of approximately equal size and equivalence. Qualified subjects will be randomly assigned to the three treatment groups based on a randomization scheme developed using the baseline plaque and gingival assessment scores and age for stratification. The study staff responsible for random assignments will be blinded to the product treatments. Allowance will be made for members of the same household co-habiting at one address to receive the same products to prevent inadvertent switch-over.

#### VIII. TEST PRODUCTS AND CLINICAL SUPPLIES

## **Test Products** Two baking soda-containing dentifrices:

containing 20% baking soda ( 1. dentifrice with 35% baking soda minus amorphous calcium phosphate (ACP) **Negative Control** 

with 0% baking soda

Clinical Supplies The sponsor will provide the following items to the study site:

- 3916-23A Toothpaste
- 3916-23B Toothpaste
- 3916-23C Toothpaste

\*\* The 18-week visit will include only: Diary review, product weights, product distribution, sensory evaluation, adverse events, update of inclusion/exclusion and any medical changes.

Toothbrushes -2 per subject to be dispensed at the baseline and 3 month visits.

#### **Packaging and Labeling**

The dentifrice products will be provided in white labeled 6.0 oz. tubes to protect the blind. The assigned dentifrice product, along with a toothbrush, timer, subject diaries and instructions will be distributed to subjects in a white bag (provided by All Sum Research) to protect the blinding of the examiner/study personnel and subjects.

The dentifrice front- and back-panel labels will include the following information:

Front Panel Label	Back Panel Label
Subject #:  Tube #:  Product Code: XXXX-XX  Gimgivitis Study#: ST-7700  Anti-Cavity Toothpaste  Not For Sale  Study Participant Use Only  Investigational natural health product to be used only by a qualified investigator for the purpose of this Clinical Study.  MFG Date: XXXX Lot# XXXXXX  Exp. Date: 01/2019  Net contents: 6.0 oz	Product contains: 0.24% Sodium Fluoride (inactives will be listed for each test article)  Warnings: Keep out of reach of children. If more than used for brushing is accidently swallowed, get medical help or contact a Poison Control Center right away.  Directions: Do not swallow. See enclosed instruction sheet. Store at room temperature.  Dist. By:  All Sum Research Center Ltd  Questions / Problems  (Days)  Evening emergencies please call  Manufactured by:

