#### VI. STUDY DESIGN

This parallel group, double-blind, randomized, single center, IRB/IEC-approved study will enroll approximately 320 subjects to ensure that approximately 100 subjects per group (300 subjects total) will complete the 6-month study. The Study Examiner will screen for subjects that meet the enrollment criteria. Subject group stratification will be based on smoking and tobacco use. Subjects will be randomly assigned to one of three dentifrice treatment groups. Oral soft and hard tissue examinations, gingivitis, bleeding and plaque assessments will be done at baseline and after 6 weeks and 3- and 6-months. Following an initial supervised tooth brushing, subjects will brush unsupervised with their assigned toothpaste at home for the 6-month treatment phase of the study, 2 times daily for 1 minute per brushing. Subjects will be provided with a timer and will maintain a daily diary of their brushing and record any oral effects they experience. Compliance will be assessed by subject diary and weight-loss of returned test products at each visit. The examiner will be blinded to the product codes/identification and product assignments.

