#### PRODUCT USE COMPLIANCE

To ensure compliance with product use, each subject will complete a daily diary indicating the time of each tooth brushing for the 6-month duration of the study. The diary will also provide space for voluntary comments about the products and any effects the subject experiences.

The subjects will be requested to return their dentifrice, toothbrush, timer and diary at each exam visit for a compliance check. The dentifrice products will be weighed at initial dispensation and at all subsequent visits to assess product use and subject compliance with study requirements. Based on product weights, subjects who appear to be out of compliance will again be shown how to apply a full ribbon of product to their toothbrush and will be reminded to brush two times daily. To maintain blinding, each subject's dentifrice tube will be inspected to confirm that the overlabel has not been removed. The subjects will also be questioned at each site visit to confirm they have not removed the label and identified the product being used.

Following 2-weeks of product use, subjects will be contacted by phone to remind them of the product use instructions and study instructions.

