#### XII. ADVERSE EXPERIENCES

#### **Adverse Event Definition and Handling**

An adverse event (AE) is any unexpected or serious medical occurrence in a clinical investigation subject during the study, whether or not related to the study product. An AE is therefore any unfavorable and unintended sign (including an abnormal laboratory finding), symptom or disease temporally associated with the administration of an investigational product, whether or not related to that investigational product. An unexpected AE is one of a type not identified in nature, severity, or frequency in the investigational product summary.

Adverse events will be reported to the sponsor within 24 hours and the sponsor will be notified immediately of any serious adverse event.

All adverse events observed by the Investigator and/or reported by the subject will be recorded throughout the entire study and documented. The Investigator will be asked to make a judgment on all adverse events as to their severity and possible relation to the study treatments.

More specifically, adverse events would include:

- Any unexpected event not seen before study initiation.
- Any pre-existing event that recurs with increased intensity or increased frequency subsequent to initial product treatment.

All adverse events should be recorded on the appropriate case report form, including date of onset, severity, duration, treatment and follow-up observation.

The following definitions will be used for grading severity of adverse events:

- Mild Either asymptomatic, or subject is aware of the sign, symptom or event, but it is easily tolerated.
- Moderate Discomfort enough to cause interference with usual activity and may warrant intervention.
- Severe Incapacitating with inability to do usual activities.

The Investigator will assess the likelihood that there is a reasonable possibility of a causal relationship between a study product and the adverse event. This will be captured using the following criteria: product related, non-product

related, non-product related but protocol related. The causal relationship to the product will be assessed as: definitely related, probably related, probably related, probably not related or definitely not related.

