#### **Efficacy Analysis**

The primary analysis will be conducted on the population of subjects who complete all study visits. A secondary analysis will be conducted on the intent to treat population; that is, at each time point, all subjects who completed both the baseline evaluation and that evaluation will be included in the analysis. Additional subsets of the subject

population may be analyzed for informational purposes only. Other than the subject inclusion criterion, all analyses will be conducted identically as follows:

For each examination and each index, subjectwise mean Index scores will be obtained by calculating the average of the index scores evaluated at all individual measurement sites within the mouth. In addition to these 'whole-mouth' scores, subjectwise scores will also be obtained by calculating the average index scores over selected subsets of sites within the mouth. These subsets will include: Proximal sites; Marginal sites (MGI and GBI only); Gingival sites (PI only); Facial sites; Lingual sites; Posterior sites; Anterior Facial sites; and Anterior Lingual sites.

All statistical analyses will be based on the subjectwise Index scores. Separate analyses will be performed based on the subjectwise whole-mouth scores, as well as the subjectwise scores obtained from each of the selected subsets of the mouth.

The primary endpoints employed for the treatment comparisons in this study will be the month 6 Index scores. Additional analyses will be conducted on the Index scores collected at other time points. The comparison of the study treatments will employ an analysis of covariance (ANCOVA) model, with the associated baseline Index score included as a covariable. The ANCOVA model will include the factors: subject, treatment, and baseline Index score. Post-ANCOVA pairwise treatment comparisons of the adjusted means will be performed using t-tests utilizing Tukey's adjustment for multiple comparisons. Within-treatment comparisons of the mean baseline Index scores to the mean month 6 (or other post-baseline time point) Index scores will be performed using paired t-tests.

The comparison of the study treatments at baseline for each index will be performed using the same model described above, without the inclusion of the covariable.

All statistical tests of hypotheses will be two-sided, and employ a level of significance of  $\alpha = 0.05$ .

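### The planned back-panel label lists each paste's own inactives, so an intact label could show subjects and tube-handling staff whether the tube is baking soda or control

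*Combined protocol and SAP*

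**What the plan says.** Section VI (Study Design) calls the trial double-blind and says of the examiner: "The examiner will be blinded to the product codes/identification and product assignments". Section VIII describes two test pastes, with 20% and 35% baking soda, and a negative control "with 0% baking soda".

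Under Packaging and Labeling, white-labelled tubes in a white bag are used "to protect the blinding of the examiner/study personnel and subjects". The back-panel text in the same section begins "Product contains: 0.24% Sodium Fluoride (inactives will be listed for each test article". Sodium fluoride is the only ingredient it names for all tubes.

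Product Use Compliance has two blinding checks. Staff inspect each tube to see that the overlabel is still on, and "The subjects will also be questioned at each site visit to confirm they have not removed the label and identified the product being used". Staff also handle the tubes for another purpose: "The dentifrice products will be weighed at initial dispensation and at all subsequent visits".

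**The concern.** The plan relies on the label to conceal the product, yet the label is to carry information that differs between arms in the ingredient under test. A subject could learn which type of paste they have by reading the tube, without removing anything. Staff who weigh or inspect tubes could do the same.

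The examiner who scores MGI, GBI and PI is separately blinded, and nothing here suggests that this fails. The exposed routes are these:

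- **Brushing.** After the first supervised session, all brushing is at home and unsupervised (section IX). Knowing the paste type could change the behaviour that produces the index scores.
- **Who is analysed.** Under Efficacy Analysis, "The primary analysis will be conducted on the population of subjects who complete all study visits". If knowledge of the paste affects withdrawal, it affects membership of the primary analysis set. The secondary set, called intent to treat, also requires the later evaluation, so it does not recover subjects who leave before month 6.
- **Safety and subjective data.** Safety is part of the primary objective. Sensory effects and many adverse events are self-reported, and the month 6 questionnaire is subjective. On causality, "The Investigator will be asked to make a judgment on all adverse events as to their severity and possible relation to the study treatments".
- **Staff conduct.** Staff re-instruct subjects whose tube weights suggest poor compliance, and could do so differently by arm if they know the paste type.

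**Working it through.** The plan gives no figure to reproduce. The main check sets its statements side by side.

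1. The packaging is meant to keep both study personnel and subjects blinded (Packaging and Labeling).
2. The label is to list inactives for each test article (same section). The natural reading is a separate list per paste.
3. Baking soda makes up 20%, 35% and 0% of the three pastes (section VIII). Only sodium fluoride is named as common to all, so baking soda would be expected among the other listed ingredients of the two test pastes.
4. From 2 and 3, a truthful list names baking soda on two products and omits it on the third. If only the two test products carried a list, its absence would mark the control equally well.
5. The overlabel inspection tests whether the label has been removed. A subject who read an intact label passes it. The question about identifying the product may reveal the problem afterwards but does not prevent it.
6. No section describes a common list, a masked list, or a list kept off the tube.

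Steps 1 and 4 conflict, and the safeguard in step 5 does not resolve the conflict.

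The exposure can be counted. These are routine study volumes and say nothing about the size of any bias.

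| Quantity | Inputs and source | Result |
|---|---|---|
| Subjects with baking soda on the label | 320 enrolled, three roughly equal groups (sections V, VII): 320 × 2/3 | about 213 |
| Subjects without | 320 / 3 | about 107 |
| Tubes per subject | one each at baseline, 6 weeks, 3 months and 18 weeks (section X) | 4 |
| Tubes in all | 320 × 4, assuming no withdrawals | 1,280 |
| Brushings per subject | 2 per day × 7 × 26, taking 6 months as 26 weeks | 364 |
| Weighing visits per subject | baseline, 6 weeks, 3 months, 18 weeks, 6 months (Study Schedule) | 5 |
| Weighing occasions | 300 × 5 for the planned completers; 320 × 5 if all complete | 1,500 to 1,600 |
| Planned non-completion | (320 − 300) / 320 | 6.25% |

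The 6.25% is the sponsor's enrolment allowance. It shows how many subjects are expected to fall outside the primary analysis, not how many would leave because of the label.

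**The case against.** The strongest reply is that the key step is inferred. The remark about inactives is a drafting note in a label template, the final label is not shown, and the plan never says that baking soda will be among the inactives. The term test article is also undefined, and section VIII separates test products from the negative control. This stands as a limit on certainty. It does not remove the conflict, because the natural reading yields the cue and nothing in the plan rules it out.

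Second, seeing an ingredient is not the same as knowing the arm. Each subject sees one label, and members of one household may be given the same product, which limits comparison at home. A subject would also need to know that baking soda is under test. What subjects are told is not visible here; the protocol says only that a trial description will be public. This too stands as an uncertainty, though it is a weak basis for a claim of double-blinding.

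Third, the efficacy indices are scored by a blinded examiner, and brushing is supported by a timer, a diary, tube weights and a compliance question. That protects scoring, and it would show differences in paste use. It would not remove effects on brushing technique, withdrawal or self-reports.

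Fourth, the plan does not say that the staff who weigh tubes also record sensory effects or adverse events, or that the investigator reads the back panel. The staff route is therefore possible but not shown.

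Fifth, the pastes may differ in taste or texture, on which the plan is silent, so the label's added contribution is unknown. That is fair, but it is no reason to print a further cue.

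**Conclusion.** The concern holds. Followed as written, the labelling instruction would very probably print a test-versus-control cue on a tube that is supposed to conceal the product, and the planned tube inspection would not detect it. This conflicts with the double-blind statement for subjects and for staff who handle tubes. It does not show that the examiner would be unblinded or that 20% can be told from 35%.

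The conclusion assumes that each paste carries its own list and that baking soda appears on it. The direction and size of any bias cannot be derived from the documents. The point merits correction before supplies are labelled: the change is cheap then, and blinding once lost cannot be restored. Confidence is medium because the finished label is unseen.

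**What to change.** Amend Packaging and Labeling so that the label is identical across the three arms except for subject number, tube number, product code and lot details. Print one pooled list of inactives, worded as ingredients the product may contain, on the label or on the common instruction sheet, where the applicable labelling rules allow. Hold the full product-specific lists at the site for emergency use. If the sponsor already intends a common list, the section should say so.

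If the rules require product-specific lists, qualify the double-blind statement in section VI for subjects and tube-handling staff. In that case tabulate by arm the answers on product identification, the product weights and the withdrawals, all of which the trial already collects.

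The cost is a label revision before supply, with notification of the IRB/IEC and the regulator. Subjects would see ingredients that their tube may not contain, and anyone who needs the exact contents, including others in the household, would have to ask the site. Allergy to any ingredient of the test or control products is already an exclusion criterion, so for enrolled subjects a pooled list covers the same ingredients. The change removes only the ingredient list as a cue. The product code would still show which tubes share a product, and any difference in taste or texture would remain.

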#### **Study Supplies Accountability**

**Delivery and Inventory:** Immediately upon receipt of study supplies at the clinical site, study personnel will account for all products and return the designated copy of "Test Supply Delivery Form" to the Sponsor acknowledging receipt of the test materials. The Investigator shall assure that appropriate records are maintained of: number of study products received, distribution to study participants, or other disposition, including dates, type of test articles, and product code numbers. The Investigator must account for any significant discrepancy and/or deficiency.

Any interim shipments will be inventoried by the Investigator or his / her designee. For all interim shipments, Test Supply Delivery Forms will be completed. The original will be returned to the Sponsor and the Investigator will retain a copy.

**Storage:** Study supplies will be maintained under secure, dry, room temperature conditions, until assignment to subjects.

**Return of Study Supplies:** At the conclusion of the study, All Sum Research will collect and inventory all dispensed products and complete the "Test Supply Delivery and Return Form" for returned study products. All used and unused products will then be returned to the Sponsor Clinical Study Coordinator listed on the study protocol at the following address:

#### IX. TREATMENT REGIMEN

Qualified subjects meeting all inclusion and exclusion criteria will be provided with their assigned dentifrice, a manual toothbrush, a timer, a subject diary, and a subject instruction sheet at baseline. Subjects will be instructed to apply a full-brush length of the toothpaste and to brush in their usual manner for 1 minute (using the timer provided by the study site), 2 times daily (morning and evening), using only the assigned dentifrice and the toothbrush provided for the 6-month duration of the study. Subjects will be instructed on the use of the timer and must

demonstrate understanding of use while at the study site. After tooth brushing, subjects may rinse their mouth with tap water if they normally do so. The first 1 minute brushing at the baseline visit will be supervised at the study site to ensure that the subject understands the instructions. All subsequent brushings will be at home and unsupervised.

#### PRODUCT USE COMPLIANCE

To ensure compliance with product use, each subject will complete a daily diary indicating the time of each tooth brushing for the 6-month duration of the study. The diary will also provide space for voluntary comments about the products and any effects the subject experiences.

The subjects will be requested to return their dentifrice, toothbrush, timer and diary at each exam visit for a compliance check. The dentifrice products will be weighed at initial dispensation and at all subsequent visits to assess product use and subject compliance with study requirements. Based on product weights, subjects who appear to be out of compliance will again be shown how to apply a full ribbon of product to their toothbrush and will be reminded to brush two times daily. To maintain blinding, each subject's dentifrice tube will be inspected to confirm that the overlabel has not been removed. The subjects will also be questioned at each site visit to confirm they have not removed the label and identified the product being used.

Following 2-weeks of product use, subjects will be contacted by phone to remind them of the product use instructions and study instructions.

#### X. STUDY PROCEDURE

#### Screening/Baseline Visit

Male and female subjects selected from the study site's database and prescreened potential subjects will report to the study site where they will read and sign the informed consent prior to enrollment. Subjects will be asked about demographics, medical history, general health status and current medication usage, and the information will be recorded. Prior to exam visit, subjects will refrain from oral hygiene the morning of their visit and will refrain from eating, drinking and smoking for approximately 4 hours prior to their visit.

The subjects will provide a sensory evaluation for safety purposes and they will fill out a product use questionnaire. They will be asked if they are currently experiencing any problems such as burning, stinging, irritation, etc., and if so, the nature of the effect, severity and onset time (if known) will be recorded on the CRF.

A qualified dental examiner will first perform an oral soft and hard tissue examination (OST), followed by a gingival assessment (Lobene Modified Gingival Index (MGI)), gingival bleeding assessment (Gingival Bleeding Index (GBI)) and plaque assessment (Soparkar Modification of the Turesky Modification of Quigley-Hein Plaque Index (PI)).

Next, qualified subjects will be given one tube of their randomly assigned dentifrice (baseline weight recorded), a toothbrush, timer, Subject Diary, and a Subject Instruction Sheet. They will be instructed to apply a ribbon of dentifrice along the entire length of the toothbrush bristles, and to brush 2 times daily (morning and evening) for 1 minute per brushing. Subjects will be given a timer to use for a timed 1 minute at home brushing and a diary to record the time of each brushing and any comments they may have about their brushing experience. To ensure that the subjects understand the use instructions, the subjects will do the first brushing at the site under supervision.

The subjects will be instructed not to use any other oral hygiene products. However, subjects who currently use dental floss will be able to continue use, whereas non-flossers will be instructed not to start flossing during the study. Subjects will be scheduled to return in approximately 6 weeks and will be instructed to refrain from any oral hygiene procedures the morning of their visit and to refrain from eating, drinking and smoking for approximately 4 hours prior to their visit. They will be advised to follow the instructions carefully and return to the 6-week visit with their assigned toothpaste, toothbrush, timer and diary for their next examination. Subjects will receive a reminder call prior to their 6-week visit.

